6.6 Adverse Event Analysis by Study Week

Treatment-emergent adverse events during the 12-week Treatment Period will be assigned to study week intervals based on the Study Day of onset as follows.

Study Week(s)	Study Day Range
Week 1	1 – 7
Week 2	8 - 14
Week 3	15 – 21
Week 4	22 - 28
Weeks 5 – 8	29 - 56
Weeks 9 – 12	≥ 57

6.7 **Derived Datasets**

The study database will include the following derived datasets which will be used for the analyses described in this SAP.

- Subject Characteristics for all subjects who participated in the study: one record per subject with demographic, baseline characteristic, analysis population and subgroup variables.
- Study Drug Exposure for the Safety Dataset: For LCIG subjects, one record per subject for each exposure variable (morning dose, extra dose, etc.) and each planned assessment time with the prescribed dose and actual dose. For OMT subjects, one record per subject per medication.
- Efficacy Endpoints for the All Randomized Dataset: one record per subject for each variable and each planned assessment time with the baseline value, time point value, and change from baseline value for the UDysRS, PDQ-8, CGI-C, UPDRS Part II, UPDRS Part III, mAIMS, King's PD Pain Scale, and "ON" time without troublesome dyskinesia, "OFF" time, "ON" time with

> troublesome dyskinesia and "ON" time without dyskinesia as measured by PD Diary.

A Derived Dataset Specification that includes a detailed description of the dataset's structure and variables will be developed for each derived dataset.

7.0 Subject Disposition, Baseline Characteristics and **Concomitant Medications**

7.1 **Subject Disposition**

An overall summary of the disposition of all screened subjects will be prepared. The total number of subjects in each of the following categories as well as the number at each site will be presented: screened, screen failed; randomized to OMT group, prematurely discontinued treatment from OMT group, completed the planned 12 weeks of treatment in OMT group; randomized to LCIG group, prematurely discontinued treatment from LCIG group, completed the planned 12 weeks of treatment in LCIG group. The total number of subjects in LCIG group in each of the following categories as well as the number at each site will be presented: Randomized, No NJ/PEG-J placed, NJ placed, prematurely discontinued treatment during NJ, PEG-J placed, prematurely discontinued treatment during 12-week Treatment Period, prematurely discontinued treatment during commercial transition, transit to commercial.

An additional summary of screen failures will be prepared with the number and percentage of screened subjects who screen failed overall and for each specific screen failure reason.

Additional summaries of premature study drug discontinuations during the first 12 weeks of treatment for both treatment groups, during the transition period (LCIG group only) and during the entire study (including first 12 weeks and transition period for LCIG group only) will be prepared for the Safety Dataset with the number and percentage of subjects who prematurely discontinued for any reason, for each specific primary reason, and for each specific reason.

[figure not shown]

A listing will be prepared of all randomized subjects who are not included in the primary efficacy analysis. The listing will include each subject number and reason for exclusion.

7.2 **Demographic and Baseline Characteristics**

The following demographic and baseline characteristics will be summarized by treatment group and for overall subjects in the safety dataset unless otherwise specified.

- Gender (male/female)
- Race (white, black, American Indian/Alaska native, native Hawaiian or other Pacific Islander, Asian, Other, Multi-Race)
- Ethnicity (Hispanic or Latino, ne)
- Age (years)
- Age category ($< 65, \ge 65$)
- Age category ($< 75, \ge 75$)
- Weight for all subjects (kg)
- Weight for all male subjects (kg)
- Weight for all female subjects (kg)
- Height (cm)
- Body mass index (BMI, kg/m^2)
- Body mass index category ($< 25 \text{ kg/m}^2, \ge 25 \text{ kg/m}^2$)
- Mini-Mental State Examination (MMSE) total score
- Parkinson's disease duration (years)
- Motor fluctuation duration (years)
- Parkinson's disease duration category (< 10 years, \geq 10 years)
- Time from Parkinson's disease diagnosis to start of first levodopa medication • (vears)
- Proportion of subjects meeting each of the following United Kingdom Parkinson's Disease society (UKPDS) Brain Bank diagnostic criteria for PD
 - Diagnosis of bradykinesia
 - Diagnosis of muscular rigidity

- Diagnosis of 4 6 Hz resting tremor
- Diagnosis of postural instability

Alcohol and nicotine use will also be summarized. For alcohol use the number and percentage of subjects who are drinkers, ex-drinkers and non-drinkers (defined as those who have never been a drinker) will be presented. For nicotine use the number and percentage of users, ex-users and non-users (defined as those who have never been a user) will be presented. A subject reporting multiple use categories for the different types of nicotine (cigarettes, pipes, cigars and chewing tobacco) will be counted in the nicotine use category closest to user.

Categorical variables will be summarized with the number and percentage of subjects in each category. Continuous variables will be summarized with descriptive statistics (number of non-missing observations, mean, standard deviation, median, minimum and maximum).

7.3 Medical History

The conditions/diagnoses recorded in medical/surgery history eCRF will be coded using the most current version of the Medical Dictionary for Regulatory Activities (MedDRA). Medical/surgical history data will be summarized by primary MedDRA system organ class (SOC) and preferred term (PT) for each treatment group and overall subjects in the Safety Dataset. Subjects reporting more than one condition/diagnosis for a given PT will be counted only once for that term. Subjects reporting more than one condition/diagnosis within an SOC will be counted only once for the SOC total. Subjects reporting more than one condition/diagnosis will be counted only once in the overall medical history total. The SOCs will be presented in alphabetical order and the PTs will be presented in alphabetical order within each SOC.

7.4 Prior and Concomitant Medications

Medications prescribed for the treatment of Parkinson's disease (anti-PD medications) will be identified by the investigator and will be entered into the database and summarized

separately from other medications. All medications will be coded using the World Health Organization (WHO) dictionary and will be summarized by generic name.

Summaries of 3 categories of anti-PD medications (anti-PD motor symptom medications, anti-PD non-motor symptom medications, and anti-PD sleep medications) will be prepared for the Safety Dataset for the following periods:

- from V1 prior to Day 1
- during the 12-week Treatment Period (start date before or on the last date of the 12-week Treatment Period and end date on or after Day 1)

Each summary will include the number and percentage of subjects who took each specific medication, each incremental number of medications (1, 2, 3, 4, 5, and 6 or more) and each cumulative number of medications (1 or more, 2 or more, 3 or more, 4 or more, and 5 or more). For the summary of anti-PD motor symptom medications, the count will be for medications other than levodopa-carbidopa.

The following summaries of other medications will be prepared for the Safety Dataset.

- Other medications prior to treatment (start date before Day 1)
- Other medications during the 12-week Treatment Period (start date before or on the last date of the 12-week Treatment Period and end date on or after Day 1)

Each summary will include the number and percentage of subjects who took each specific medication and the number who took 1 or more medications.

8.0 **Treatment Exposure and Compliance**

Summaries of treatment exposure and compliance will be prepared for the Safety Dataset.

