Following optional NJ and/or PEG-J placement on Study Day 1 and, at the discretion of the Investigator, the subject may begin initiation and titration of LCIG infusion on Study Day 1 once tube placement is confirmed. All other oral anti-PD medications other than amantadine must be stopped prior to LCIG initiation. The dose of LCIG should be adjusted to obtain the optimal clinical response for the individual subject. Optimal clinical response, or optimization, is defined as maximizing the functional "On" time during the day and minimizing the number of "Off" episodes (bradykinesia) and the time the subject is "Off." In addition, optimization minimizes "On" time with troublesome dyskinesia. This determination is made by the Investigator. The dosage procedures for LCIG are described in Section 5.5.1 Treatments Administered.

Oral levodopa medication may only be used as a supplement during the night following discontinuation of the LCIG infusion. During the day it should be used ONLY as rescue medication in case of acute deterioration, presumably caused by failure of the tubes and/or the pump or the onset of an acute illness.

It may take several days to optimize LCIG treatment. In some subjects, optimization may take longer and if required, at the discretion of the investigator or local practitioner, subjects may be admitted and remain hospitalized for the duration of the titration period. For those subjects with an NJ placement they may or may not continue the NJ Period at home until the PEG-J is inserted.

During the initial titration phase, extra doses may be administered by the Investigator or subject every hour. Pump programming should only be done by trained site personnel and all dose changes must be approved by the Investigator. After the nightly discontinuation of LCIG drug administration, levodopa-DDI (DOPA decarboxylase inhibitor) tablets may be taken up to 2 hours (for oral LC-IR) or 4 hours (for oral LC-CR)

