1, 6, 7, 9, 15 – 18, 24, 25	To reduce the risk to subjects or others and/or to exclude underlying conditions that would compromise the ability to make causality assessments relative to LCIG treatment for safety events
5, 8, 10 – 14, 19, 22 – 23	To ensure safety of the subjects throughout the study
2-4, 20-21, 28	To exclude, or to minimize, the number of medications or other factors that could interfere with the LCIG treatment, or could add unnecessary variance or bias to safety evaluations

Christian Cel/Carbidopa Levodopa Enteral Suspension M15-535 Protocol Amendment 1 EudraCT 2016-001403-23

26 - 27

The impact of LCIG treatment on pregnancies and lactation is unknown

5.2.3 **Prior and Concomitant Therapy**

Any medication or vaccine (including over-the-counter or prescription medicines, vitamins and/or herbal supplements) that the subject is receiving from 30 days prior to signing the Informed Consent Form, or receives during the study, must be recorded along with the reason for use, date(s) of administration including start and end dates, and dosage information including dose, route and frequency.

The AbbVie TA MD should be contacted if there are any questions regarding concomitant or prior therapies.

5.2.3.1 **Prior Therapy (Prior to Randomization)**

All medications taken by the subject during the study and from 30 days prior to signing the Informed Consent Form are to be recorded in the eCRF.

5.2.3.2 **Concomitant Therapy**

All changes to concomitant medications must be carefully documented on the Concomitant Medication eCRF.

Allowable Medications

Anti-Parkinsonian Medications

The following classes of anti-Parkinsonian medications will be allowed during the study:

Levodopa formulations

- For the OMT group, all levodopa formulations are allowed
- For the LCIG treatment group:

- o levodopa formulations can only be used at nighttime (the 8 hours when the pump is not in use) or as rescue medication
 - long-acting levodopa formulations can only be used at nighttime (at least 4 hours prior the next day's morning dose)
 - short-acting levodopa formulations with the exception of formulations containing entacapone can only be used at nighttime (at least 2 hours prior to the next day's morning dose) or as rescue medication

Dopamine agonists (not including apomorphine continuous infusion or PRN injection)

MAO-B inhibitors

Anti-cholinergics

Amantadine –

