5.2.3.4 Post Infusion Night Time Therapy (LCIG Treatment Group Only)

Those subjects randomized to the LCIG Treatment group will be permitted to selfadminister their typical night-time regimen of oral LC-IR or levodopa-carbidopa continuous-release (LC-CR) following the daily discontinuation of the 16-hour infusion, only if they were taking this during the 30 day stable medication period during screening and the dose must remain unchanged. The Investigator will provide a prescription for the doses of oral LC-IR or LC-CR that the subject takes on a regular nightly basis. After the nightly discontinuation of LCIG treatment drug administration, levodopa-DOPA decarboxylase inhibitor (DDI) tablets or similar such as Levodopa + carbidopa = Sinemet, LD + CD + entacapone = Stalevo, Levodopa + Benserazide = Madopar may be taken up to 2 hours (for oral LC-IR) or 4 hours (for oral LC-CR) prior to the administration of the next morning dose of LCIG and should not be counted as rescue. The subject should record all oral levodopa-carbidopa tablets on the Subject Dosing Diary on the assigned days.

Those subjects randomized to the OMT group will remain on their normal, stable nighttime regimen if applicable.

5.2.4 **Contraception Recommendations and Pregnancy Testing**

If female, subject must be either postmenopausal defined as:

• Age > 55 years with no menses for 12 or more months without an alternative medical cause.

• Age < 55 years with no menses for 12 or more months without an alternative medical cause AND an FSH level > 40 IU/L.

OR

- Permanently surgically sterile (bilateral oophorectomy, bilateral salpingectomy or hysterectomy).
- Practicing at least one of the following methods of birth control, on Study Day 1 (or earlier) through at least 30 days after the last dose of study drug.
 - Combined (estrogen and progestogen containing) hormonal contraception (oral, intravaginal, transdermal) associated with the inhibition of ovulation, initiated at least 1 month prior to Study Day 1.
 - Progestogen-only hormonal contraception (oral, injectable, implantable) associated with inhibition of ovulation, initiated at least 1 month prior to Study Day 1.
 - o Bilateral tubal occlusion/ligation.
 - Vasectomized partner(s), provided the vasectomized partner has received medical assessment of the surgical success and is the sole sexual partner of the women of child bearing potential (WOCBP) trial participant.
 - o Intrauterine device (IUD).

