9.6 Efficacy Subgroup Analysis

To determine if the following factors have an impact on the response to treatment, subgroup analyses will be conducted on the change from baseline to final visit on the UDysRS total score:

- Gender
- Age category ($< 65, \ge 65$)
- Duration of Parkinson's disease (< 10 years, \geq 10 years)
- Total daily dose of levodopa (< 1250 mg, ≥ 1250 mg) at the end of initial LCIG titration for the LCIG group and in the first set of dosing diary for the OMT group
- Number of anti-PD medications other than levodopa taken at any time during the week prior to randomization (0 or 1, 2 or more)

The subgroup analyses will be performed using an ANCOVA model contain treatment, country, and subgroup as main effects, treatment by subgroup interaction, and baseline score as the covariate. The LS mean change for each stratum of the subgroup with associated 95% confidence interval will be presented.

The descriptive statistic summary described for the UDysRS total scores will also be prepared for each subgroup stratum.

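### SAP 7.4 can overstate add-on anti-PD drug use: its count leaves out only levodopa-carbidopa, and in the LCIG arm it treats drugs stopped for LCIG initiation as on-treatment use

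*SAP*

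**What the plan says.** SAP 7.4 codes medications by generic name. For the Safety Dataset it plans rows for each specific anti-PD drug and for the number of drugs taken (1, 2, 3 and so on, and *1 or more*, *2 or more* and so on). Two rules govern these tables.

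- Count rule: "For the summary of anti-PD motor symptom medications, the count will be for medications other than levodopa-carbidopa".
- Period rule for the 12-week Treatment Period: "start date before or on the last date of the 12-week Treatment Period and end date on or after Day 1".

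The subgroup factor in SAP 9.6 excludes more: "Number of anti-PD medications other than levodopa taken at any time during the week prior to randomization".

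The protocol does not confine levodopa to levodopa-carbidopa. Section 5.2.3.2 states: "For the OMT group, all levodopa formulations are allowed". Section 5.2.3.4, on night-time therapy in the LCIG arm, lists "Levodopa + Benserazide = Madopar" among its examples.

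Day 1 is the day after randomization for OMT and the day of first NJ or PEG-J placement for LCIG (SAP 4.2 and 6.2). For the LCIG arm, Protocol 5.1.2.2 says: "All other oral anti-PD medications other than amantadine must be stopped prior to LCIG initiation". It also notes that when an NJ tube is placed passively, the radiological check may come around 48 hours later. Drugs other than apomorphine, levodopa products and amantadine may be restarted, but not in the first 28 days.

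**The concern.** LCIG starts without other anti-PD drugs apart from amantadine, while OMT subjects stay on their regimen. A reader of an open-label UDysRS difference will want to know how much non-levodopa co-treatment each arm received during the 12 weeks, and SAP 7.4 is the planned summary of that.

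Two features of the rules can make the answer too high. A subject whose only drug is levodopa-benserazide appears to be on an add-on drug, while the same subject on levodopa-carbidopa does not. And an LCIG subject who stopped everything as required can appear in the same row as one who needed a drug restarted weeks later. The second mix-up matters more, because whether LCIG held without add-on drugs is one of the things the table should show.

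**Working it through.** The plan gives no figure on this point, so there is none to reproduce. The check applies the two rules literally to simple cases.

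**Count rule.** Number of drugs counted for one subject:

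| Drugs taken | SAP 7.4 | SAP 9.6 wording |
|---|---|---|
| Levodopa-carbidopa only | 0 | 0 |
| Levodopa-benserazide only | 1 | 0 |
| Both of these | 1 | 0 |
| Levodopa-benserazide and one MAO-B inhibitor | 2 | 1 |
| Levodopa-carbidopa and one MAO-B inhibitor | 1 | 1 |

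The difference is always +1 for a levodopa-benserazide user and never negative. It can arise in OMT, where any levodopa product is allowed, and in LCIG, where levodopa-benserazide is named for night use. The levodopa-carbidopa-entacapone product does not produce the difference: SAP 7.4 counts it as one drug, and it still counts as one if levodopa is left out and its entacapone part is counted.

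**Period rule.** A drug is counted if its start is no later than the last treatment day (nominally Day 84) and its end is on or after Day 1. There is no Day 0 (SAP 6.2). For an LCIG subject:

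| Drug history | Test | Counted? |
|---|---|---|
| Last taken the day before Day 1 | end = −1, below 1 | No |
| Stopped on Day 1, before the first infusion | end = 1 | Yes |
| Stopped on Day 3, before a first infusion delayed by about 48 hours (Day 1 + 2 days) | end = 3 | Yes |
| Restarted on Day 29 | start = 29, below 84; end after Day 1 | Yes |

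Rows 2 and 3 can comply with the stop-before-initiation sentence in Protocol 5.1.2.2, yet they are treated exactly like row 4. The per-drug rows use the same period rule and carry the same error. In OMT the rule does no harm: the regimen continues by design, so a drug taken on Day 1 is genuinely on-treatment use.

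The rules can act together in LCIG. Protocol 5.5.1.2 bases the starting dose on the oral levodopa taken immediately before tube placement, so an oral levodopa stop date on or about Day 1 is plausible. If that product was levodopa-benserazide, the subject gains one counted drug.

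**Size.** Two inputs are missing: the share of subjects on a levodopa product such as levodopa-benserazide, and the share of LCIG subjects with a stop date on or after Day 1 but before the first infusion. As an assumption, let a share f of about 30 subjects per arm (Protocol synopsis) be affected and take no other qualifying drug. The rise in the *1 or more* row is then 30 × f:

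- f = 0: 0 subjects
- f = 10%: 3
- f = 25%: 7.5, about 8
- f = 50%: 15
- f = 100%: 30

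These are upper limits for a given f. An affected subject who also takes a genuinely counted drug is already in that row, and Protocol 5.6.1 says most subjects take other anti-PD drugs besides levodopa.

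**The case against.** The strongest reply is that the tables are descriptive. Protocol 8.1.2 rules out testing on them, and the counts enter neither the primary MMRM nor the gatekeeping sequence. That stands, and it sets the weight of the point.

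The period rule also follows the plan's own definitions. The table uses the Safety Dataset, and the LCIG safety treatment period begins on the day of first tube placement (Protocol 8.1.1), so a drug taken that day was taken within the period. That is correct as a definition. It does not help a reader separate drugs being stopped from drugs being added.

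The per-drug rows will show levodopa-benserazide by name, so an attentive reader can undo the count rule in part. They do not help with the period rule. Tapering over up to 14 days may also mean that many drugs end before Day 1, in which case they are classified correctly. The documents do not say how often.

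A reader might infer several stronger things that the documents do not support.

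- That the inflation falls on OMT. It does not fall on OMT alone, because levodopa-benserazide is named for LCIG night use too.
- That the Day 1 rule distorts OMT. It does not, as shown above.
- That this table is the only account of what OMT consisted of. SAP 8.4 summarizes total daily levodopa dose by visit for both arms, and the exposure dataset in SAP 6.7 holds a record per OMT subject per medication.
- That true LCIG add-on use must be below 25%, because over 75% needed only levodopa-carbidopa in the 54-week study described in Protocol 3.0. That is a different study, and here subjects on amantadine at randomization continue it unless stopping is medically indicated.

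**Conclusion.** The point holds as a minor one. SAP 7.4 can overstate add-on anti-PD drug use: through the count rule in either arm, and through the period rule in the LCIG arm only. The error can only be upward. No primary or secondary result is affected.

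Whether it occurs, and how far, depends on how many subjects use levodopa-benserazide or a similar product and on the recorded stop dates. The documents give neither, so the 30 × f figures illustrate scale and are not an estimate. If no subject uses such a product and every stop date precedes Day 1, nothing is misstated.

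**What to change.** In SAP 7.4, replace the exclusion of levodopa-carbidopa by an exclusion of any levodopa formulation, matching SAP 9.6. State in both sections that the entacapone part of a fixed combination counts as one drug.

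For the LCIG arm, classify on-treatment use relative to the first LCIG infusion by either route: the end date is later than the date of that infusion, or the start date is on or after it. Under this rule the Day 1 and Day 3 stops in the second table drop out, and the Day 29 restart and continued amantadine stay in. Show use after Day 28 separately. The SAP should name the day from which that split counts, because the protocol dates the 28-day restriction from PEG placement in some places and from LCIG initiation in another. It should also say how to handle a Safety Dataset subject who had a tube placed but never received an infusion. The OMT period rule can stay.

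Separately, Protocol 5.2.3.4 names the levodopa-carbidopa-entacapone product for night use in the LCIG arm, while Protocol 5.2.3.2 and its Table 3 exclude it there. These passages must be reconciled, since they determine what can appear in the table.

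Drug names and start and end dates are already recorded (Protocol 5.2.3), as is the first infusion date (SAP 8.7). The cost is SAP wording and programming. The downside is one more table split.
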